7.1 Pharmacokinetic Analysis Set

The PK analysis set (PKAS) includes all randomized subjects who have received at least one dose of omecamtiv mecarbil and have at least one evaluable omecamtiv mecarbil PK concentration. This analysis set will be used in analyses of all the PK endpoints.

7.2 Full Analysis Set

The full analysis set (FAS) includes all randomized subjects who have received at least one dose of IP (omecamtiv mecarbil or placebo). Efficacy analyses of the secondary and exploratory endpoints will be performed on FAS. All subjects will be analyzed according to their randomized treatment assignment.

7.3 Safety Analysis Set

Safety analyses will be performed on Safety Analysis Set which is defined as the same as the full analysis set. For safety analyses, subjects will in general be analyzed according to their randomized treatment group assignment. If a subject receives the same treatment throughout the study that is different from their randomized treatment group, then the subject will be analyzed by the actual treatment group/schema (note: randomized to 25 mg BID, randomized to 37.5 mg BID but received 25 mg BID, and randomized to 50 mg BID but received 25 mg BID will all be treated as different schemas due to PK levels).

7.4 Completer Analysis Set

The completer analysis set (CAS) includes all subjects in FAS who complete IP administration. This analysis set will be used in sensitivity analysis of the secondary endpoint.

7.5 Subgroup Analyses

The echocardiographic secondary endpoint will be summarized and analyzed by the following subgroups:

IVRS stratification factor

- presence or absence of atrial fibrillation/flutter at randomization.

Baseline Covariates

- age at study enrollment (< 65 vs. ≥ 65 years)
- sex (male vs. female)
- LVEF (< median vs. ≥ median)
- body mass index (BMI) (< median vs. ≥ median)
- NT-proBNP (< median vs. ≥ median)
- Coronary artery disease (CAD) (presence vs. absence)

8. Interim Analysis and Early Stopping Guidelines

No interim analyses are planned for this study.

An external independent DMC will formally review the accumulating data from Amgen's ongoing omecamtiv mecarbil studies to facilitate detection of any increased risk for harm to subjects (eg, unexpected PK concentration due to PK variability). The DMC will review unblinded data approximately every month while subjects are receiving IP.

Based on the totality of evidence, the DMC will make an overall recommendation to the sponsor whether to continue the study according to the protocol or whether to make any changes (eg, including, but not limited to, dose change or stopping enrollment). To protect the status of the blind and to minimize potential operational bias, analyses for the DMC will be provided by the independent biostatistics group which is external to Amgen and supported by designated Amgen staff (eg, Clinical Pharmacology Lead in Protocol Section 10.3), if needed. Details will be provided in the DMC charter.

9. Data Screening and Acceptance

9.1 General Principles

The objective of the data screening is to assess the quantity, quality, and statistical characteristics of the data relative to the requirements of the planned analyses.

9.2 Data Handling and Electronic Transfer of Data

The Amgen Global Study Operations-Data Management (GSO-DM) department will provide all data to be used in the planned analyses. This study will use the RAVE database.

An Analysis Dataset for PK Concentrations (ADPC) will be provided to the appropriate CPMS representative from Global Biostatistical Sciences.

9.3 Handling of Missing and Incomplete Data

9.3.1 Patterns of Missing Data

Subjects may be missing specific data points for various reasons. In general, data may be missing due to a subject's early withdrawal from study, a missed visit, or non-evaluability of a data point or an endpoint at a particular point in time. All attempts will be made to capture missing or partial data for this trial prior to the database lock.

The frequency and pattern of missing data for efficacy endpoints will be assessed through descriptive summaries of the measurements over time.

For all time-to-event endpoints, there will be no imputation of the data, except for incomplete dates of the events. For all other endpoints, unless specified otherwise, missing data will not be imputed.

9.3.2 Handling of Incomplete Dates

Adverse event and concomitant medication (collected start date data) with completely or partially missing start dates will be queried. After the issue is queried, if the date is still incomplete with year only or year and month only, the start date will be imputed as described in the table below.

Imputation Rules for Incomplete Dates

	Missing	Imputation	Exception
Start date (AE and concomitant edication)	Day	1	Default to Study Day 1 if an event starts the same year and month as Study Day 1
	Day/Month	1-Jan	Default to Study Day 1 if an event started the same year as Day 1

9.4 Detection of Bias

This study has been designed to minimize potential bias by the use of stratified randomization of subjects into treatment groups and the use of blinding. Other factors that may bias the results of the study include:

- major protocol deviations likely to impact the analysis and interpretation of the efficacy endpoints
- subject level unblinding before final database lock and formal unblinding
- DMC related analyses

Important protocol deviations likely to impact the analysis and interpretation of the efficacy endpoints will be tabulated in the Clinical Study Report (CSR).

Any unblinding of individual subjects prior to formal unblinding of the study will be documented. The impact of such unblinding on the results observed will be assessed.

For DMC related analyses, details of access to subject level treatment assignments are provided in the protocol, Section 10.3.

Additional sensitivity analyses may be included to assess the impact of potential biases on the primary and secondary endpoints. If any sensitivity analyses are required to evaluate potential biases in the study's conclusions, then the sources of the potential biases and results of the sensitivity analyses will be documented in the CSR.

9.5 Outliers

Various methods, including univariate summaries, histograms, scatter plots, box plots, and line graphs, may be used to identify outliers in key safety and efficacy variables. Extreme data points will be identified during the blinded review of the data prior to database lock. Such data points will be reviewed with clinical data management to ensure accuracy. The primary analyses will include outliers in the data. Sensitivity analyses may be undertaken if extreme outliers for a variable are observed.

9.6 Distributional Characteristics

Distributional assumptions for the primary and secondary endpoints will be assessed. Generally, no other transformations will be applied besides those specified in [Section 10](#). The use of alternative methods will be fully justified in the CSR.

9.7 Validation of Statistical Analyses

Programs will be developed and maintained, and output will be verified in accordance with current risk-based quality control procedures.

Tables, figures, and listings will be produced with validated standard macro programs where standard macros can produce the specified outputs.

The production environment for statistical analyses consists of Amgen-supported versions of statistical analysis software; for example, the SAS System version 9.3 or later.

10. Statistical Methods of Analysis

10.1 General Principles

The final analysis will be conducted when all subjects have either completed all the scheduled study visits or have early terminated from the study. At that time, the database will be cleaned, processed and a snapshot will be taken; the study will also be unblinded. All endpoints will be analyzed based on this snapshot.

No formal hypothesis will be tested, and all statistical approaches are hypothesis-generating. Descriptive statistics will be presented for all endpoints.

Subject disposition, demographics, baseline characteristics and exposure to IP will be summarized.

Summary statistics for continuous variables will include number of subjects, mean, median, SD, or standard error, lower and upper quartiles, minimum, and maximum. For PK parameters, coefficient of variation (CV) will also be included. For categorical variables, frequency and percentage will be presented. Unless specified otherwise, all confidence intervals for estimates will be 2-sided with a significance level of 0.05.

Subjects will be analyzed based on their randomized or received treatment group assignment as described in [Section 7](#).

Missing data handling is specified in [Section 9.3](#).

For the secondary endpoint SET, sensitivity analyses using the CAS will be conducted to explore the robustness of selected results.

10.2 Subject Accountability

The number and percent of subjects who were randomized, received investigational product, completed investigational product, discontinued investigational product and reasons for discontinuing, completed study, and discontinued study and reasons for discontinuing will be summarized by treatment group.

Key study dates for the first subject enrolled, last subject enrolled, last subject end of study, and last subject end of investigational product will be presented.

The number of subjects included in and excluded from each analysis set will be summarized.

10.3 Important Protocol Deviations

Important Protocol Deviations (IPDs) categories are defined by the study team before the first subject's visit and updated during the IPD reviews throughout the study prior to database lock. These definitions of IPD categories, sub-category codes, and descriptions will be used during the course of the study. Eligibility deviations are defined in the protocol.

10.4 Demographic and Baseline Characteristics

Demographic and baseline disease characteristics will be summarized by randomized treatment group and overall for all randomized subjects using descriptive statistics. If multiple races have been reported for a subject, the subject will be categorized as multiple race.

Demographics include: age, sex, race and region.

Baseline disease characteristics include:

- Physical measurements (height, weight, BMI) and vital signs
- Medical history (HF specific and non-specific, including presence of CAD, HF etiology and LVEF)
- HF related medication history including HF treatment at baseline
- Baseline ECG HR and select electrocardiographic parameters, including SET, SV, LVESD and LVEDD
- Baseline laboratory measurements (HF specific and non-specific, including NT-proBNP and troponin)
- The IVRS stratification factor (presence or absence of atrial fibrillation/flutter).

10.5 Analyses of Primary Endpoints

The primary endpoints are omecamtiv mecarbil PK parameters $C_{predose}$ and AUC, collected in the study ([Section 4.1.1](#)).

All data for PK analyses will be extracted from a secure folder and mapped via a clinical connector into the Pharsight Knowledgebase Server (PKS) system (Pharsight Corporation, St. Louis, MO).

Omecamtiv mecarbil plasma concentration-time data will be analyzed by noncompartmental methods using Phoenix WinNonlin (Pharsight Corporation, St. Louis, MO) and will be stored in the validated PKS system. Concentration values less than or

equal to the lower limit of quantification (LLOQ, 1 ng/mL) will be set to zero in the analysis dataset. In the PK data analysis, LLOQ value (zero) will be excluded.

Actual doses administered and actual or nominal sampling times post drug administration will be used in the noncompartmental analysis. Nominal times will be used for presenting data in graphs and tables. All pharmacokinetic parameters and summary statistics will be presented to 3 significant digits.

Summary statistics of PK parameters will include mean, standard deviation and CV%; median and range; geometric mean and CV% of geometric mean. Each pharmacokinetic parameter will be summarized by dose level and sampling time.

In the pharmacokinetic analysis, the following parameters will be estimated:

- Observed maximum concentration (C_{\max})
- Observed time to achieve C_{\max} (t_{\max})
- Observed concentration prior to next dose (C_{predose})
- Area under the plasma concentration-time curve (AUC_t) calculated by linear trapezoidal method
- Ratio of $C_{\max} / C_{\text{predose}}$

Individual concentration-time data will be tabulated and presented graphically. Mean concentration-time profiles for each dose will be provided.

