10.1.2 Analysis Sets

The PK analysis set (PKAS) includes all randomized subjects who have received at least one dose of omecamtiv mecarbil and have at least one evaluable omecamtiv mecarbil PK parameter (C_{max} , $C_{predose}$). This analysis set will be used for analyses of all the PK endpoints, unless significant protocol deviations have affected the data or if key dosing or sampling information are missing, in which case a modified PKAS will be used.

The full analysis set (FAS) includes all randomized subjects who have received at least one dose of IP (omecamtiv mecarbil or placebo). This set will be used for all analyses of non-PK endpoints.

The completers analysis set is a subset of the FAS and includes subjects who have completed IP administration. The completers analysis set will be used for sensitivity analyses.

Approved

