10.5.2 Primary Endpoint

The primary endpoints are the omecamtiv mecarbil PK parameters C_{predose} and AUC, collected in the study ([Section 10.1.1.1](#)).

In the PK analysis, all plasma concentrations below the quantifiable limits will be assigned the value of zero. For any data excluded from the analyses, specific reasons will be provided.

Individual omecamtiv mecarbil concentration-time data and summary statistics will be tabulated for omecamtiv mecarbil. Individual, mean, and SD concentration-time data may be plotted. The PKAS will contain all subjects for whom at least one PK parameter (C_{max} , C_{predose}) can be adequately estimated. PK parameters will be calculated using non-compartmental methods. Actual dosing and sampling times will be used for calculation of PK parameters. Descriptive statistics will be generated for each PK parameter for each treatment.

Individual PK parameters will be summarized descriptively at each scheduled assessment, in the primary analysis set of PKAS.

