10.8.6 Exposure to Concomitant Medication

Concomitant medications will be coded by the World Health Organization Drug (WHO DRUG) dictionary. The number and proportion of subjects receiving oral medications of interest will be summarized by medication category, preferred term and regimen dose, unit and frequency at baseline and EOS for each treatment group.

11. Changes From Protocol-specified Analyses

During the initial development of this document, it was realized that there are protocol-specified analyses that cannot be implemented/Performed and the protocol is not required to be amended. HF treatment at baseline will not be included as a baseline covariate. HF treatment, including BB, ACEi or ARB, is one of the expansion phase inclusion criteria and therefore the study is not expected to support subgroup analysis of no HF treatment at baseline. These changes will also be documented in the Clinical Study Report.

The definition of the PKAS was clarified to require one evaluable PK concentration rather than PK parameter as stated in the protocol.

12. Literature Citations / References

13. Data Not Covered by This Plan

This SAP does not address the analysis for the secondary objective

- to explore the potential relationship between omecamtiv mecarbil exposure and changes from baseline in SET

14. Appendices

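### For the primary PK endpoints, the SAP excludes below-LLOQ values that the protocol keeps as zero and omits the protocol's modified PK analysis set, and it declares neither change

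*SAP*

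**What the plan says.** **Values below the limit of quantification (BLQ).** Protocol Section 10.5.2 states that "all plasma concentrations below the quantifiable limits will be assigned the value of zero", and adds: "For any data excluded from the analyses, specific reasons will be provided". SAP Section 10.5 takes two steps. Values less than or "equal to the lower limit of quantification (LLOQ, 1 ng/mL) will be set to zero in the analysis dataset"; then "In the PK data analysis, LLOQ value (zero) will be excluded". The SAP's cut-off also takes in a value exactly at the LLOQ, where the protocol's covers only values below it.

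**Analysis set.** Protocol Section 10.1.2 uses the PK analysis set (PKAS) unless significant deviations have affected the data or "if key dosing or sampling information are missing, in which case a modified PKAS will be used". SAP Section 7.1 has a single set: "This analysis set will be used in analyses of all the PK endpoints". It requires one evaluable concentration but does not say what makes a concentration evaluable.

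**Declared changes.** On PK, SAP Section 11 records only this: "The definition of the PKAS was clarified to require one evaluable PK concentration rather than PK parameter as stated in the protocol". The BLQ exclusion and the loss of the modified PKAS are not listed.

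**The concern.** Cpredose at weeks 2, 4, 12 and 16, together with the week 8 AUC, is the primary endpoint, and a programmer cannot follow both documents. Off-drug samples are foreseeable. Protocol Section 8.1 lets subjects stop investigational product and stay in the study, and Section 6.2.1.2 has mandatory withholding rules with possible rechallenge.

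For such samples the natural question is whether the subject was dosed on schedule. The modified PKAS was the only protocol provision that looked at deviations and at dosing and sampling information. Without it, the one explicit exclusion left in the SAP works on the measured value. A long interruption drops out because the assay reads low. For a shorter interruption, nothing in the SAP sends the analyst to the dosing record except the definition of Cpredose in SAP Section 6.3, as the concentration at the end of the 12-hour interval. What is at stake is the reported mean, its CV, and the number of subjects behind each primary summary.

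**Working it through.** **1. The plan's own precision table.** Inputs (Protocol Section 10.2, SAP Section 3.2): SD 40 to 90, N = 19, two-sided 95%. Half-width = 1.96 × SD / √19. For SD 40, 50, 60, 70, 80 and 90 this gives 17.99, 22.48, 26.98, 31.48, 35.97 and 40.47, matching the stated 18.0, 22.5, 27.0, 31.5, 36.0 and 40.5. The table is sound and is unaffected by this point; it fixes 19 as the planned number per arm.

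**2. Excluding a BLQ value versus keeping it as zero.** Suppose k of 19 values at a visit are BLQ and the rest have mean M. The SAP mean is M and the protocol mean is M × (19 − k)/19. The documents give neither k nor M, so both are assumptions; the percentages do not depend on M.

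| k | Protocol mean below SAP mean (k/19) | SAP mean above protocol mean (k/(19 − k)) |
|---|---|---|
| 0 | 0% | 0% |
| 1 | 5.3% | 5.6% |
| 2 | 10.5% | 11.8% |
| 3 | 15.8% | 18.8% |
| 4 | 21.1% | 26.7% |

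Illustration with M = 150 ng/mL, SD = 70 and k = 2:
- SAP: mean 150, CV 46.7%, half-width 1.96 × 70/√17 = 33.3.
- Protocol: mean 150 × 17/19 = 134.2. SD = √{[16 × 70² + 17 × (150 − 134.2)² + 2 × 134.2²]/18} = 81.2. CV 60.5%, half-width 1.96 × 81.2/√19 = 36.5.

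**3. What a BLQ trough means.** Inputs: LLOQ 1 ng/mL (SAP Section 10.5) and mean half-life 17.1 to 23.2 h (Protocol Section 2.2.2.1, IV dosing in healthy volunteers). Time to reach the LLOQ = log2(C0/1) × half-life.
- From 50 ng/mL: 5.64 × 17.1 = 96.5 h to 5.64 × 23.2 = 130.9 h, or 4.0 to 5.5 days.
- From 200 ng/mL (the up-titration threshold, used only as a scale): 130.7 to 177.3 h, or 5.4 to 7.4 days.
- From 277 ng/mL (simulated mean Cmax at 25 mg BID, Protocol Table 1): 138.7 to 188.2 h, or 5.8 to 7.8 days.

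So a BLQ value at weeks 2 to 16 in an active-arm subject points to roughly 4 to 8 days without drug.

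**4. What the assay rule does not catch.** From an assumed trough of 150 ng/mL, the remainder is 150 × 2^(−t/half-life). After a further 24 h this is 56.7 to 73.2 ng/mL, and after 72 h it is 8.1 to 17.5 ng/mL. Both are far above 1 ng/mL. The assay rule does not remove them; only a rule based on dosing times would.

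**5. BLQ on schedule.** Protocol Section 6.2.1.1 sets doses 12 ± 3 h apart. At the 15 h end, 2^(−15/17.1) = 0.54 to 2^(−15/23.2) = 0.64 of a concentration remains. A trough taken on schedule at steady state should almost never be BLQ.

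**The case against.** The strongest reply has four parts.

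- **The samples the SAP drops are ones a dosing-based rule would drop as well.** By steps 3 and 5, a BLQ trough is almost certainly off schedule. The aim is PK under chronic twice-daily dosing, and averaging an off-drug zero into that mean may distort it more than leaving it out. This stands. It means the 5% per value measures disagreement between the documents, not error in the SAP.
- **SAP Section 6.3 already ties Cpredose to the end of a 12-hour interval.** A sample taken days after the last dose does not meet that definition, and the PKAS asks for an evaluable concentration. This stands in part. The definition is relevant, but the SAP gives no time window, no meaning for evaluable, and no step that checks samples against dosing records.
- **Excluding zeros has an evident purpose.** The SAP adds geometric means, which zeros make uncomputable, and drug-naive Day 1 predose samples will be BLQ and are not a primary time point. Both are reasonable readings, but the exclusion is not limited to either.
- **The practical impact may be nil.** Table 2 sends early discontinuers to end-of-study assessments, which include no PK sample. SAP Section 9.4 allows sensitivity analyses for bias, and no hypothesis is tested. This limits the expected size, but Section 9.4 is discretionary and Protocol Section 8.1 still allows continued visits off drug.

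A reader might go further and infer that the SAP summaries depend on an assay limit and not on whether the subject was dosed. The documents do not support that: the limit is a crude marker of not being dosed, and the protocol's zero rule ignores dosing records too. A reader might also calculate how far a partly washed-out sample would pull down the geometric mean and treat it as an expected bias. That assumes samples outside the Section 6.3 definition are retained, and no count of them is given.

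**Conclusion.** The point holds as two undeclared departures from the protocol in the primary PK analysis: BLQ zeros excluded rather than kept, and the modified PKAS omitted. The second matters more, because it removes the only explicit exclusion based on deviations and on dosing and sampling information.

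The effect is nil if no week 2 to 16 sample is BLQ or off schedule. Otherwise, each BLQ value among 19 separates the two arithmetic means by about 5%. This rests on 19 evaluable subjects per arm and an assumed BLQ count. Reading BLQ as several days off drug rests on a half-life from IV dosing in healthy volunteers, which may not carry over to modified-release tablets in heart failure. Neither direction nor size of bias can be claimed from the documents. The difference at exactly 1 ng/mL is negligible but should be harmonised. The correction is worth making because it concerns a stated primary-endpoint rule and costs almost nothing.

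**What to change.** In SAP Sections 7.1 and 10.5:

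- Restore the protocol's modified PKAS.
- Define an evaluable Cpredose sample from the recorded dosing and sampling times, consistent with SAP Section 6.3 and the protocol's existing 12 ± 3 h dosing interval, and not from the assay value.
- For evaluable samples, state one BLQ rule, with BLQ meaning strictly below the LLOQ: zero for the arithmetic mean and median, geometric mean on positive values only, and the BLQ count shown at each visit.
- List every excluded sample with its reason, as Protocol Section 10.5.2 requires.
- Record any remaining departure from the protocol in SAP Section 11.

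Once evaluability is set by dosing times, the BLQ rule should rarely act; it serves as a stated backstop. The cost is SAP wording and one listing, using times the study already collects. The downside is that a few off-schedule samples leave the main table.
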